Appendix 2. Detailed Dose Escalation/De-Escalation Scheme for mTPI Design

Escalation/De-escalation algorithms for total number of patients treated at the current dose level (current and previous cohorts)

- With 2 patients treated at current dose level:
 - 0 DLT -> escalate;
 - 1 DLT -> remain at the same dose;
 - 2 DLTs -> de-escalate and consider current dose as intolerable.

- With 3 patients treated at current dose level:
 - 0 DLT -> escalate;
 - 1 DLT -> remain at the same dose;
 - 2 DLTs -> de-escalate;
 - 3 DLTs -> de-escalate and consider current dose as intolerable.

- With 4 patients treated at current dose level:
 - 0 DLT -> escalate;
 - 1-2 DLTs -> remain at the same dose;
 - 3-4 DLTs -> de-escalate and consider current dose as intolerable.

- With 5 patients treated at current dose level:
 - 0 DLT -> escalate;
 - 1-2 DLTs -> remain at the same dose;
 - 3 DLTs -> de-escalate;
 - 4-5 DLTs -> de-escalate and consider current dose as intolerable.

- With 6 patients treated at current dose level:
 - 0-1 DLT -> escalate;
 - 2 DLTs -> remain at the same dose;
 - 3 DLTs -> de-escalate;

- 4-6 DLTs -> de-escalate and consider current dose as intolerable.
- With 7 patients treated at current dose level:
 - 0-1 DLT -> escalate;
 - 2-3 DLTs -> remain at the same dose;
 - 4 DLTs -> de-escalate;
 - 5-7 DLTs -> de-escalate and consider current dose as intolerable.
- With 8 patients treated at current dose level:
 - 0-1 DLT -> escalate;
 - 2-3 DLTs -> remain at the same dose;
 - 4 DLTs -> de-escalate;
 - 5-8 DLTs -> de-escalate and consider current dose as intolerable.
- With 9 patients treated at current dose level:
 - 0-1 DLT -> escalate;
 - 2-4 DLTs -> remain at the same dose;
 - 5-9 DLTs -> de-escalate and consider current dose as intolerable.
- With 10 patients treated at current dose level:
 - 0-1 DLT -> escalate;
 - 2-4 DLTs -> remain at the same dose;
 - 5 DLTs -> de-escalate;
 - 6-10 DLTs -> de-escalate and consider current dose as intolerable.
- With 11 patients treated at current dose level:
 - 0-1 DLT -> escalate;
 - 2-5 DLTs -> remain at the same dose;
 - 6-11 DLTs -> de-escalate and consider current dose as intolerable.

- With 12 patients treated at current dose level:
 - 0-2 DLTs -> escalate;
 - 3-5 DLTs -> remain at the same dose;
 - 6 DLTs -> de-escalate;
 - 7-12 DLTs -> de-escalate and consider current dose as intolerable.

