3.1.5. Criteria for Dose Escalation

Compared to the traditional mTPI method, the proposed mTPI method for this protocol includes stopping rules and dose escalation/finding criteria, which prevents the target DLT rate to reach $\geq 33\%$ for determining the MTD. This proposed mTPI method, targeting a DLT rate of 27.5% and an acceptable DLT interval (22.5% to 32.5%), will be utilized in Part 1 dose escalation/finding phase, and will also be used to monitor the DLTs so as not to cross toxicity boundaries in the expansion of a cohort. In this process, the upper limit of the DLT rate to determine a MTD will be $< 33\%$. This proposed mTPI method is more conservative than the traditional toxicity probability interval (TPI) method.

The mTPI method relies upon a statistical probability algorithm, calculated using all patients treated in the current dose level to determine one of the following dose-finding decisions: the subsequent dose should be escalated, maintained at the current dose, or de-escalated in the next cohort of 1-4 patients, or the trial should be terminated (Table 1).

Table 1. Dose Escalation/De-Escalation Decision Rules

DLT	n=2	n=3	n=4	n=5	n=6	n=7	n=8	n=9	n=10	n=11	n=12
0	E	E	E	E	E	E	E	E	E	E	E
1	S	S	S	S	E	E	E	E	E	E	E
2	D	D	D	S	S	S	S	S	S	S	E
3		U	U	D	D	S	S	S	S	S	S
4			U	U	U	U	D	S	S	S	S
5				U	U	U	U	U	D	S	S
6					U	U	U	U	U	U	U
7						U	U	U	U	U	U
8							U	U	U	U	U
9								U	U	U	U
10									U	U	U
11										U	U
12											U

Actions to be taken: D = De-escalate the dose; E = Escalate the dose; S = Stay at the dose. U = Unacceptable toxicity.

Initially, dose cohorts may consist of 1-2 patients in the single agent dose escalation in Part 1A. When a DLT is observed, additional patients will be enrolled and dose escalation decision will follow the mTPI criteria. Table 2 showing escalating doses with a 100% to 150% increase from the previous dose in dose levels (DLs). In later cohorts it is anticipated that total daily dose level increases may approximate 100% or less depending on emerging available clinical data, including safety/tolerability, laboratory, PK and PD findings.

The total daily dose will be administered once a day (QD) or in divided doses of either two (BID) or three times a day (TID).

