9.2. Statistical Methods and Properties

9.2.1. Statistical Methods for Dose Escalation/De-Escalation

Many alternative designs have been proposed to the standard 3+3 design for Phase 1 dose escalation studies that improve its accuracy, efficiency and statistical validity.

The traditional mTPI design (Ji et al., 2010)²⁹ uses a Bayesian statistics framework and a beta/binomial hierarchical model to compute the posterior probability of 3 dosing intervals that reflect the relative difference between the toxicity rate of each dose level to the target rate ($p_T = 0.275$). If the toxicity rate of the currently used dose level is far smaller than p_T , the mTPI will recommend escalating the dose level; if it is close to target probability (p_T), the mTPI will recommend continuing at the current dose; if it is far greater than p_T , the mTPI will recommend de-escalating the dose level. These rules are conceptually similar to those used by the 3+3 design, except the decisions of an mTPI design are based on posterior probabilities calculated under a coherent probability model. The proposed modified TPI method for this protocol includes stopping rules and dose escalation/finding criteria, which prevents the target DLT rate to reach $\geq 33\%$ for determining the MTD. This proposed mTPI method is more conservative than the traditional TPI method. Being a rule-based design, mTPI automatically and appropriately tailors dose-escalation and de-escalation decisions for different studies with different toxicity parameters. More importantly, all the dose-escalation and de-escalation decisions for a given study can be pre-calculated under the mTPI design and presented in a two-way table (See [Section 3.1.5](#)). Thus, compared to other advanced model-based designs published in the literature, the mTPI design is logistically less complicated and easier to implement. Recently, a Phase 1 study based on the mTPI design has been published (Fanale, 2011).³⁰

Decision rules are based on calculating unit probability mass (UPM) of 3 dosing intervals corresponding to under, proper, and over dosing in terms of toxicity. Specifically, the underdosing interval is defined as $(0; p_T - e_1)$, the over-dosing interval $(p_T + e_2, 1)$, and the proper-dosing interval $(p_T - e_1, p_T + e_2)$, where e_1 and e_2 are small fractions. Based on the safety profile of PF-06873600 as a single-agent in study (C3661001), e_1 is selected as

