0.05 and e_2 is selected as 0.05. Therefore, the target interval for the DLT rate is (0.225, 0.325).

The 3 dosing intervals are associated with 3 different dose-escalation decisions. The underdosing interval corresponds to a dose-escalation (E), overdosing corresponds to a dose de-escalation (D), and proper dosing corresponds to remaining at the current dose (S). Given a dosing interval and a probability distribution, the unit probability mass (UPM) of that dosing interval is defined as the probability of a patient belonging to that dosing interval divided by the length of the dosing interval. The mTPI design calculates the UPMs for the 3 dosing intervals, and the one with the largest UPM informs the corresponding dose-finding decision, which is the dose level to be used for future patients. For example, if the under-dosing interval has the largest UPM, the decision will be to escalate, and the next cohort of patients will be treated at the next higher dose level. Ji et al. (2010)²⁹ have demonstrated that the decision based on UPM is optimal in that it minimizes a posterior expected loss (ie, minimizes the chance of making a wrong dosing decision). The decision rules to “dose escalate” (E), “no change in dose” (S), “dose de escalate” (D) or “dose de escalate, unacceptable toxicity” (U) are described in [Section 3.1.5](#) (see [Table 1](#)).

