Appendix 7.1. Japan Specific Requirements

Japan Participation: Japan Lead-in Cohort

The Japan lead-in cohort (J-LIC) will be conducted at sites in Japan and added as a sub-cohort to this study. The primary and secondary objectives are to assess the safety, tolerability and PK of PF-06873600. **CCI**

See Section 2 for more information about the endpoints of this study. For participants enrolled into the J-LIC, PF-06873600 will be administered orally BID on a continuous basis as a single agent. At least 3 patients, and if necessary up to 6 patients, will be enrolled in this cohort overall.

Figure 10. Japanese Lead-in Cohort Schema

*Dose de-escalation or discontinuation of patient enrollment would be considered

The dose of J-LIC will be the RDE of monotherapy (ie, 25 mg IR) that was determined to be tolerable based on mTPI in a non-Japanese population in Part 1A. At this RDE, no DLTs were reported. While dose escalation and de-escalation decision will not be selected for J-LIC, DLT evaluation will follow the mTPI using a beta (0.5,0.5) as a prior DLT distribution on the RDE for Japanese patients; therefore, evaluation results on the RDE cohort responding to DLT outcomes in J-LIC are the same as for non-Japanese patients in Table 1. The sample size for J-LIC will be 3-6 patients. If no patients in the first 3 patients experienced DLT in Cycle 1, this dose level will be declared tolerable for Japanese patients (Actions to be taken in Table 1 will be "E"). If one patient experienced DLT in the first 3 patients (Actions to be taken in Table 1 will be "S"), 2-3 additional patients will be treated with the same dose. If the additional patients do not experience DLTs in Cycle 1, this dose

level will be declared tolerable for Japanese patients (Actions to be taken in [Table 1](#) will be “S”). If 1 DLT is observed in the additional patient group (ie, 2 of 5 patients), 1 additional patient (total 6 patients) will be enrolled. Japan participation in Part 2 will be determined based on the safety data review meeting comprised of the investigator and the sponsor, in order to ensure the safety of Japanese patients. If DLT is observed in ≥ 2 of 3 patients or ≥ 3 of 6 patients, dose de-escalation, or discontinuation of patient enrollment will be considered.

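### Protocol Table 1 and Appendix 2 disagree in four of 88 mTPI cells, neither reproduces the stated rule, and the exclusion threshold and DLT-evaluability rule differ between sections

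*Protocol*

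**What the plan says.** **Two grids.** Section 3.1.5 of the protocol contains "Table 1. Dose Escalation/De-Escalation Decision Rules", with entries E (escalate), S (stay), D (de-escalate) and U (unacceptable toxicity) for 2 to 12 patients. SAP Section 2.1.4 repeats it as Table 2. Appendix 2 lists the decisions again in words. Its block for four patients reads "1-2 DLTs -> remain at the same dose" and then "3-4 DLTs -> de-escalate and consider current dose as intolerable". (The first line also appears in the five-patient block, where it agrees with Table 1.)

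**Which one is cited.** Section 9.2.1 says that "all the dose-escalation and de-escalation decisions for a given study can be pre-calculated under the mTPI design and presented in a two-way table" and refers to Section 3.1.5 for that table. For the Japan lead-in cohort, Appendix 7.1 says that "evaluation results on the RDE cohort responding to DLT outcomes in J-LIC are the same as for non-Japanese patients in Table 1". No operative section cites Appendix 2, and no clause says which prevails.

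**The rule behind the grid.** Sections 9.2.1 and 9.2.2 give a target of 27.5%, an interval of 22.5% to 32.5%, a Beta(0.5,0.5) prior, the action with the largest unit probability mass (UPM), and an exclusion threshold of 0.95. A U dose and all higher doses are closed for the rest of the trial, whereas doses already tested may otherwise be used again. SAP Section 4.2.1 gives the threshold as 0.975.

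**Evaluability.** Protocol 3.1.5 requires 75% of planned doses unless a DLT came first. Protocol 9.1 and SAP 6.3 keep a patient below 75% if the shortfall was due to drug toxicity. SAP 2.1.4 makes a similar exception for treatment-emergent toxicity.

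**The concern.** DLTs and the MTD are the primary outcome of Part 1, and the attraction of this design is that every decision can be read from one pre-computed table. Two versions that disagree remove that property. After 2 DLTs in 4 patients, one page keeps treating at the dose and the other steps down. After 2 in 2, one page closes the dose for good and the other leaves it open to re-entry.

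If neither version follows from the stated prior and threshold, a reader of the report cannot reconstruct the decisions either. The evaluability difference adds a second gap: SAP 9.2.1 summarises DLTs on the per-protocol set, so the reported denominator may not be the one that drove the dose decision.

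**Working it through.** **1. Compare the two grids.** The number of cells is 3 + 4 + ... + 13 = 88. They differ in four. The last two columns apply the stated rule.

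| DLTs/n | Table 1 | Appendix 2 | Rule at 0.95 | Rule at 0.975 |
|---|---|---|---|---|
| 2/2 | D | U | U | U |
| 2/4 | D | S | S | S |
| 4/7 | U | D | U | D |
| 6/12 | U | D | U | D |

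SAP Table 2 agrees with Table 1 in these cells, so this is not a fault of text extraction.

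**2. Recompute the stated rule.** With x DLTs in n patients the posterior is Beta(0.5 + x, 0.5 + n - x). UPM is the posterior probability of an interval divided by its length (0.225, 0.100 and 0.675 for under-, proper and over-dosing). U applies if Pr(p > 0.275) exceeds 0.95.

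- 2/2: Beta(2.5, 0.5), Pr(p > 0.275) = 0.985, so U at either threshold. Table 1 prints D.
- 2/4: UPM 0.446, 1.203, 1.154, so S, narrowly. Table 1 prints D.
- 1/5: UPM 2.261, 1.977, 0.435, so E. Both grids print S.
- 2/11: UPM 2.706, 2.362, 0.230, so E. Both grids print S.
- 4/7 and 6/12: Pr(p > 0.275) = 0.954 each, so U. Appendix 2 prints D.

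Each grid therefore matches 84 of 88 cells. Table 1 misses 2/2, 2/4, 1/5 and 2/11. Appendix 2 misses 4/7, 6/12, 1/5 and 2/11.

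**3. Try other inputs.** Priors Beta(0.5,0.5), Beta(1,1) and Beta(0.005,0.005) were each run with thresholds 0.90, 0.95 and 0.975. With Beta(1,1) and 0.95, Table 1 misses only 2/2 and 1/6:

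- 2/4 gives D (over-dosing 1.1886 against 1.1876 for proper dosing).
- 1/5 gives S (2.263 against 1.804 for under-dosing).
- 2/11 gives S (2.742 against 2.348).

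None of the nine combinations gives D at 2/2.

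**4. SAP threshold.** Under Beta(0.5,0.5), Pr(p > 0.275) is 0.954 at 4/7, 0.964 at 5/9, 0.972 at 6/11 and 0.954 at 6/12. All lie between 0.95 and 0.975. SAP Table 2 prints U in each, so it contradicts the threshold in SAP 4.2.1.

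**5. Which cells can matter for selection.** Section 9.2.2 bars a dose with an observed rate above 32.5% from being the MTD. The best possible rate after 12 patients is 4/12 = 33.3% from 4/7, and 50% at 6/12. Both fail. From 2/2 or 2/4 it is 2/12 = 16.7%, so those doses could still be chosen.

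**6. How easily the cells are reached.** Section 3.1.7 allows cohorts of 1-4 in Part 1A and 2-4 in Parts 1B and 1C. At a true DLT rate of p = 0.275:

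- 2/4 in one cohort of four: 6p²(1-p)² = 23.9% (15.4% at p = 0.20, 31.1% at p = 0.35).
- 2/4 via 1/2 in cohorts of two: 4p²(1-p)² = 15.9%.
- 2/2 in a cohort of two: p² = 7.6%.

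**7. Effect on the selected dose (illustrative).** Paired simulations fed the same outcomes to both grids, with five doses, four assumed toxicity curves, at most 12 patients per dose and two stopping choices. With D doses open to re-entry, the selected dose, counting no MTD as a result, differed in roughly 5-11% of runs with cohorts of two or four and in under 1% with cohorts of three. Section 9.2.2 also has an optional rule that, beyond 6 patients, more may be treated only if the observed DLT rate is below 32.5%. Applying it, and dropping one dose when blocked, gave 1-4.5% (cohorts of two), 0-2.4% (four) and 0% (three).

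**8. Evaluability example.** Take 3 DLTs in 4 patients, plus a fifth below 75% of doses because of drug toxicity that was not a DLT. Protocol 3.1.5 excludes the fifth: 3/4 = U. The other three sections keep that patient: 3/5 = D. The documents give no frequency for such patients.

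**The case against.** The body text and the SAP both use Table 1, so in practice one grid governs, and a safety team reviewed each decision. Two of the four conflicts cannot change the selected dose. The study was terminated on 07 September 2022, and the Japan lead-in cohort reads out at 3, 5 and 6 patients, where the grids agree. All of this stands, and it limits the point to the record. It does not rescue 2/2, which is wrong in the governing table itself.

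Three stronger readings are tempting and are not supported.

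- A reader might take Table 1's stricter cells (2/4, 1/5, 2/11) as deliberate caution, since the protocol calls its method more conservative. The documents give no such reason for these cells, and a Beta(1,1) prior produces all three. That prior is itself only an inference: Section 9.2.2 and Appendix 7.1 both print Beta(0.5,0.5). Conservatism cannot explain 2/2, which is looser than the rule.
- A reader might quote a larger effect on dose selection. Simulations that never re-enter a D dose give up to 23%, but Section 9.2.2 allows re-entry, and the optional 32.5% limit pulls the figure down.
- A reader might infer that a wrong dose was chosen or patients were over-treated. Nothing in the documents shows that a conflicting cell was reached.

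**Conclusion.** The point holds as an inconsistency in the written decision rules. Four of 88 cells conflict, and two of those (2/2 and 2/4) could bear on dose selection. Each grid departs from the stated rule in four cells. At 2/2 Table 1 is looser than the rule under every prior and threshold tried. The SAP threshold contradicts both the protocol and the SAP's own table, and one protocol section defines evaluability differently from three other places.

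The cell counts rest only on the printed grids and the stated prior, interval and threshold. The simulated effect, about 0 to 11%, depends on assumed toxicity curves, cohort size and how Section 9.2.2 is applied. It omits safety-team review and should not be read as an estimate for this trial.

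For the 25 mg immediate-release single-agent dose the protocol reports "At this RDE, no DLTs were reported". Whether a conflicting cell arose at other doses or in Parts 1B and 1C cannot be told from the documents. It should be fixed, as a matter of an accurate record and a reproducible report.

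**What to change.** - State the prior and threshold actually used to build Table 1, and say that Table 1 is the operative grid.
- Correct 2/2 in Table 1 to U.
- Make Appendix 2 and SAP Table 2 match it. Label any cell that still differs from the stated rule as a departure, without asserting that it was intended.
- Set the threshold in SAP 4.2.1 to 0.95.
- Use one DLT-evaluability rule in Protocol 3.1.5 and 9.1 and SAP 2.1.4 and 6.3. SAP 2.1.4 needs a general update: it still gives about 50 patients for Part 1, against about 75 in SAP 4.2.1.
- In the CSR, state which grid and which evaluability rule governed the decisions made, and whether 2/2, 2/4 or another conflicting cell was reached.

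The cost is wording in the protocol and SAP plus one CSR statement. Since escalation is finished, the CSR statement is the part that matters most. No patients, visits or data are added.

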Appendix 3. ECOG Performance Status*

Grade	ECOG
0	Fully active, able to carry on all pre-disease performance without restriction.
1	Restricted in physically strenuous activity but ambulatory and able to carry out work of a light or sedentary nature, eg, light house work, office work.
2	Ambulatory and capable of all self-care but unable to carry out any work activities. Up and about more than 50% of waking hours.
3	Capable of only limited self-care, confined to bed or chair more than 50% of waking hours.
4	Completely disabled. Cannot carry on any self-care. Totally confined to bed or chair.
5	Dead.

*As published in Am J Clin Oncol 5:649-655, 1982.

Appendix 4. RECIST (Response Evaluation Criteria In Solid Tumors) version 1.1 Guidelines

Adapted from *E.A. Eisenhauer, et al: New response evaluation criteria in solid tumours: Revised RECIST guideline (version 1.1). European Journal of Cancer 45 (2009) 228–247*

CATEGORIZING LESIONS AT BASELINE

Measurable Lesions

- Lesions that can be accurately measured in at least one dimension.
- Lesions with longest diameter twice the slice thickness and at least 10 mm or greater when assessed by CT or MRI (slice thickness 5-8 mm).
- Lesions with longest diameter at least 20 mm when assessed by Chest X-ray.
- Superficial lesions with longest diameter 10 mm or greater when assessed by caliper.
- Malignant lymph nodes with the short axis 15 mm or greater when assessed by CT.

NOTE: The shortest axis is used as the diameter for malignant lymph nodes, longest axis for all other measurable lesions.

Non-measurable disease

Non-measurable disease includes lesions too small to be considered measurable (including nodes with short axis between 10 and 14.9 mm) and truly non-measurable disease such as pleural or pericardial effusions, ascites, inflammatory breast disease, leptomeningeal disease, lymphangitic involvement of skin or lung, clinical lesions that cannot be accurately measured with calipers, abdominal masses identified by physical exam that are not measurable by reproducible imaging techniques.

- **Bone disease:** Bone disease is non-measurable with the exception of soft tissue components that can be evaluated by CT or MRI and meet the definition of measurability at baseline.
- **Previous local treatment:** A previously irradiated lesion (or lesion subjected to other local treatment) is non-measurable unless it has progressed since completion of treatment.

Normal sites

- Cystic lesions: Simple cysts should not be considered as malignant lesions and should not be recorded either as target or non-target disease. Cystic lesions thought to represent cystic metastases can be measurable lesions, if they meet the specific definition above. If non-cystic lesions are also present, these are preferred as target lesions.
- Normal nodes: Nodes with short axis <10 mm are considered normal and should not be recorded or followed either as measurable or non-measurable disease.

Recording Tumor Assessments

All sites of disease must be assessed at baseline. Baseline assessments should be done as close as possible prior to study start. For an adequate baseline assessment, all required scans must be done within 28 days prior to randomization and all disease must be documented appropriately. If baseline assessment is inadequate, subsequent statuses generally should be non-evaluable.

Target Lesions

All measurable lesions up to a maximum of 2 lesions per organ, 5 lesions in total, representative of all involved organs, should be identified as target lesions at baseline. Target lesions should be selected on the basis of size (longest lesions) and suitability for accurate repeated measurements. Record the longest diameter for each lesion, except in the case of pathological lymph nodes for which the short axis should be recorded. The sum of the diameters (longest for non-nodal lesions, short axis for nodal lesions) for all target lesions at baseline will be the basis for comparison to assessments performed on study.

- If two target lesions coalesce the measurement of the coalesced mass is used. If a large target lesion splits, the sum of the parts is used.
- Measurements for target lesions that become small should continue to be recorded. If a target lesion becomes too small to measure, 0 mm should be recorded if the lesion is considered to have disappeared; otherwise a default value of 5 mm should be recorded.

NOTE: When nodal lesions decrease to <10 mm (normal), the actual measurement should still be recorded.

Non-target Disease

All non-measurable disease is non-target. All measurable lesions not identified as target lesions are also included as non-target disease. Measurements are not required but rather assessments will be expressed as CR, Non-CR/Non-PD, PD, Non-evaluable (NE). Multiple non-target lesions in one organ may be recorded as a single item on the case report form (eg, 'multiple enlarged pelvic lymph nodes' or 'multiple liver metastases').

OBJECTIVE RESPONSE STATUS AT EACH EVALUATION

Disease sites must be assessed using the same technique as baseline, including consistent administration of contrast and timing of scanning. If a change needs to be made the case must be discussed with the radiologist to determine if substitution is possible. If not, subsequent objective statuses might be non-evaluable.

Target Disease

1. Complete Response (CR): Complete disappearance of all target lesions with the exception of nodal disease. All target nodes must decrease to normal size (short axis <10 mm). All target lesions must be assessed.
2. Partial Response (PR): Greater than or equal to 30% decrease under baseline of the sum of diameters of all target measurable lesions. The short diameter is used in the sum for target nodes, while the longest diameter is used in the sum for all other target lesions. All target lesions must be assessed.
3. Stable: Does not qualify for CR, PR or Progression. All target lesions must be assessed. Stable can follow PR only in the rare case that the sum increases by less than 20% from the nadir, but enough that a previously documented 30% decrease no longer holds.
4. Objective Progression (PD): 20% increase in the sum of diameters of target measurable lesions above the smallest sum observed (over baseline if no decrease in the sum is observed during therapy), with a minimum absolute increase of 5 mm.
5. Non-evaluable (NE): Progression has not been documented, and
 - One or more target measurable lesions have not been assessed; or
 - One or more target lesions cannot be measured accurately (eg, poorly visible unless due to being too small to measure); or
 - One or more target lesions were excised or irradiated.

Non-target disease

1. CR: Disappearance of all non-target lesions and normalization of tumor marker levels. All lymph nodes must be 'normal' in size (<10 mm short axis).
2. Non-CR/Non-PD: Persistence of any non-target lesions and/or tumor marker level above the normal limits.

3. PD: Unequivocal progression of pre-existing lesions. Generally the overall tumor burden must increase sufficiently to merit discontinuation of therapy. In the presence of SD or PR in target disease, progression due to unequivocal increase in non-target disease should be rare.
4. NE: Progression has not been determined and one or more non-target sites were not assessed or assessment methods were inconsistent with those used at baseline.

New Lesions

The appearance of any new unequivocal malignant lesion indicates PD. If a new lesion is equivocal, for example due to its small size, continued assessment will clarify the etiology. If repeat assessments confirm the lesion, then progression should be recorded on the date of the initial assessment. A lesion identified in an area not previously scanned will be considered a new lesion.

Supplemental Investigations

- If CR determination depends on a residual lesion that decreased in size but did not disappear completely, it is recommended the residual lesion be investigated with biopsy or fine needle aspirate. If no disease is identified, objective status is CR.
- If progression determination depends on a lesion with an increase possibly due to necrosis, the lesion may be investigated with biopsy or fine needle aspirate to clarify status.

Subjective Progression

Patients requiring discontinuation of treatment without objective evidence of disease progression should not be reported as PD on tumor assessment CRFs. This should be indicated on the end of treatment CRF as off treatment due to Global Deterioration of Health Status. Every effort should be made to document objective progression even after discontinuation of treatment.

Table 5. Objective Response Status at each Evaluation

Target Lesions	Non-target Disease	New Lesions	Objective status
CR	CR	No	CR
CR	Non-CR/Non-PD	No	PR
CR	NE or Missing	No	PR
PR	Non-CR/Non-PD, NE or Missing	No	PR
SD	Non-CR/Non-PD, NE or Missing	No	Stable

Table 5. Objective Response Status at each Evaluation

Target Lesions	Non-target Disease	New Lesions	Objective status
NE or Missing	Non-PD	No	NE
PD	Any	Yes or No	PD
Any	PD	Yes or No	PD
Any	Any	Yes	PD

If the protocol allows enrollment of patients with only non-target disease, the following table will be used:

Table 6. Objective Response Status at each Evaluation for Patients with Non-Target Disease Only

Non-target Disease	New Lesions	Objective status
CR	No	CR
Non-CR/Non-PD	No	Non-CR/Non-PD
NE	No	NE
Unequivocal progression	Yes or No	PD
Any	Yes	PD

Best Overall Response

The best overall response (BOR) is the best response recorded from the randomization until disease progression or death due to any cause. This is derived from the sequence of objective statuses. Objective statuses are not considered after objective progression is documented or after start of the first anticancer treatment post discontinuation of protocol treatment. BOR for each patient will be derived as one of the following categories.

- **Complete response (CR):** At least one objective status of CR documented before progression.
- **Partial response (PR):** At least one objective status of PR documented before progression.
- **Stable disease (SD):** At least one objective status of stable documented at least 6 weeks after randomization date and before progression but not qualifying as CR, PR.
- **Progressive Disease (PD):** Objective status of progression within 16 weeks of randomization, not qualifying as CR, PR or SD.

- **Non-evaluable (NE):** Progression not documented within 16 weeks after randomization and no other response category applies.

